5.8.4.3. Impact of Discontinuation Potentially Related to Treatment

The seizure frequency data of subjects who discontinue of from the trial on or before Week 6 (Visit 3) for the following reasons are potentially missing not at random (MNAR).

- AE with AEHLGT eq 'Seizures (incl subtypes)'
- WITHDRAWAL BY SUBJECT
- LACK OF EFFICACY
- LOST TO FOLLOW-UP

In this assessment, the subjects with MNAR (to be identified and documented in Section 9.5 before database lock) will be imputed by jump to reference approach.

Specifically, the missing values in each of the active group will be imputed using the multiple imputation procedure described above except that the missing observations in CVL-865 group are not constructed from the observed data in the respective groups, but rather from the observed data in the placebo group. Any missing data from the placebo group is imputed using the observed data from the placebo group. The data will be log transformed using convention log(X+1) and back transformed to conform to the multivariate normality distribution. The

proc mi data = mcmc1 (where=(((y = . or y0=.) and trt ne 'Placebo') or (trt='Placebo' and (y0 ne. and y ne .)))) seed = SEED1 nimpute = 10 minimum =0 minmaxiter = 1000 out= Out1X; mcmc chain = multiple displayinit initial=em(itprint); var y0 y; run;

Where y represents $\ln(7 \text{ day average seizure frequency over maintenance period + 1})$, y0 is $\ln(7 \text{ day average seizure frequency over the baseline period+1})$, and SEED1 is a random number. Each of these datasets will be analyzed using the same ANCOVA model through SAS PROC MIXED as described in Section 5.8.3. The results of the analyses of the datasets will be combined using PROC MIANALYZE to produce an inferential result.

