5.2. Populations for Analyses

The analysis populations are defined Table 10.

Population	Description	Analysis
All Screened Subjects	All Screened Subjects includes all subjects who signed the informed consent form.	Disposition
ITT	All randomized subjects	Disposition, Demographic and Baseline Characteristics
FAS	All randomized subjects who receive at least 1 dose of IMP. This will be the safety analysis set.	Safety analysis
mITT	All randomized subjects who receive at least 1 dose of IMP and have both baseline seizure frequency recorded in the eDiary with entry compliance $\geq 20\%$ and at least 1 post baseline entry in the seizure diary during maintenance phase.	Primary analysis set for efficacy
PK Analysis Set	All randomized subjects who receive at least 1 dose of IMP and have at least 1 measurable CVL-865 concentration	PK analysis

Table 10:Populations for Analysis

Abbreviations: FAS = full analysis set, IMP = investigational medicinal product, ITT = intent-to-treat, mITT = modified intent-to-treat, PK = pharmacokinetic.

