5.8.2. Primary Estimand

The key research question for the primary endpoint will be addressed with an estimand based on the following attributes:

- 1. Treatments: treatments as randomized regardless of the actual treatment received.
- 2. Target study population of interest: subjects in the modified intent-to-treat (mITT) population.
- 3. Endpoint (variable) of interest: RRatio over the Maintenance Phase.
- 4. Population level summary of interest: difference between CVL-865 treated and placebo subjects in RRatio over the Maintenance Phase.
- 5. Strategy for Intercurrent events (ICEs): a hypothetical strategy will be used to address intercurrent events (ICEs) of potential death, and treatment discontinuations. The data after treatment discontinuations will typically be missing or be treated as missing even if collected. Under the hypothetical strategy, these missing values as the result of ICEs of discontinuation will be assumed to follow the observed trajectory of the subject and thus the endpoint will include only eDiary based response data that occur before discontinuation of treatment. It should be noted that the use of protocol defined rescue medication will not be considered as an ICE.

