5.8.4.2. Impact of Low eDiary Entry Compliance

To evaluate the impact of subject's low compliance of eDiary entry on the results from the main analysis, a sensitivity analysis that treat these cases as missing at random will be performed. Specifically, if a subject has more than 50% of their diary entries missing over a period (baseline, maintenance, etc), the seizure frequency for that period will be treated as missing. Multiple imputations under missing at random assumption will be performed. The Markov chain method implemented in SAS PROC MI will be utilized based on the mITT population. The imputations will be performed on the logarithmic scale $(\ln(X+1))$, where X represents the 7 day average seizure frequency for a period, and back transformed to conform to the multivariate normality distribution and the imputed values will then be back transformed to the original scale. SAS PROC MI will be used to generate 10 possible imputed datasets using the following SAS code:

```
proc mi data=mcmc1 seed=SEED1 nimpute=10 minimum=0 out=Out1X;
mcmc chain=multiple displayinit initial=em(itprint);
var TRT y0 y;
run;
```

Where TRT is an indicator variable representing treatment with the two treatment groups of 'CVL-865 7.5 mg BID', 'CVL-865 25 mg BID' or 'Placebo', y represents $\ln(7 \text{ day average}$ seizure frequency over maintenance period + 1), y0 is $\ln(7 \text{ day average seizure frequency over}$ the baseline period+1), and SEED1 is a random number.

Each of these datasets will be analyzed using the same ANCOVA model through SAS PROC MIXED as described in Section 5.8.3. The results of the analyses of the datasets will be combined using PROC MIANALYZE to produce an inferential result.

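### The SAP omits the protocol's de facto sensitivity analysis of the RRatio, and its one discontinuation analysis (5.8.4.3) does not list stops for non-seizure adverse events

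*SAP*

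**What the plan says.** **Primary estimand (SAP 5.8.2).** A hypothetical strategy is used for treatment discontinuation. "The data after treatment discontinuations will typically be missing or be treated as missing even if collected". Each subject who stops is assumed to continue on the trajectory observed before the stop.

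**Protocol 9.4.1.** The main RRatio analysis uses responses before discontinuation. The same paragraph says that sensitivity analyses on all available data, labelled the de facto estimand, will be conducted.

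**SAP 5.8.4.3.** Subjects who discontinue "on or before Week 6 (Visit 3) for the following reasons are potentially missing not at random (MNAR"). The reasons are "AE with AEHLGT eq 'Seizures (incl subtypes", withdrawal by subject, lack of efficacy and loss to follow-up. It adds that "the subjects with MNAR (to be identified and documented in Section 9.5 before database lock) will be imputed by jump to reference approach". On placebo it says: "Any missing data from the placebo group is imputed using the observed data from the placebo group". The printed PROC MI call keeps placebo rows on the condition "trt='Placebo' and (y0 ne. and y ne" not missing.

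**Procedure and population.** 5.8.4.3 borrows the procedure of 5.8.4.2: "The Markov chain method implemented in SAS PROC MI will be utilized based on the mITT population". Under SAP 5.2, mITT requires "at least 1 post baseline entry in the seizure diary during maintenance phase".

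**Reuse.** SAP 5.9.4 and 5.10.3 apply the same sensitivity analyses to both key secondary endpoints.

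**The concern.** Protocol 7.3 names adverse events as a reason for stopping treatment, without limiting them to seizures. For a subject who stops because of tolerability, the primary analysis supposes that the response seen on drug would have lasted to the end of Maintenance. No data can confirm that, so a sensitivity analysis should show how far the RRatio difference depends on it.

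Two analyses could do so. The protocol's de facto analysis does not appear in the SAP, and neither Section 6 (Changes in the Planned Analyses) nor any other visible text explains why. The jump-to-reference analysis is titled for discontinuation potentially related to treatment, but its list leaves out the adverse-event stops that are not seizures. Reasons for stopping are tabulated by arm (SAP 5.7), so unequal adverse-event dropout would be seen. Its effect on the primary result would not.

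**Working it through.** **1. The plan's own figure.** Inputs from Protocol 9.2: difference -20, SD 34, two-sided alpha 0.1, 20% dropout, 50 randomised per arm. Evaluable: 50 × 0.8 = 40 per arm. Two-sample t-test power at 40 per arm is 0.832 (normal approximation 0.838). The n for 80% power is 37 per arm, and 37/0.8 = 46.25, rounded up to 47, which is within 50. The stated power of at least 80% is reproduced, and nothing here disputes it.

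**2. What each RRatio analysis does with a stop recorded as a non-seizure adverse event.**

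| SAP section | Uses post-stop data? | Tests such a stop? |
|---|---|---|
| 5.8.4.1 treatment received | No | No; it changes only the arm assignment |
| 5.8.4.2 low diary compliance | No | Only if more than 50% of entries count as missing, and then under missing at random |
| 5.8.4.3 jump to reference | No | Not by that recorded reason |
| 5.8.5 subgroups | No | No; defined by diary compliance or baseline frequency |

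**3. Could the 50% diary rule catch it?** Take a subject with a complete diary who stops on Day 30. SAP Table 3 ends Maintenance the day before early termination, so Days 15 to 29 count: 15 days. SAP 5.7.1 counts only time in the study, so compliance is 15/15 = 100% and the rule is not triggered. Against the planned 56 days, 41/56 = 73% would be missing and the rule would apply, but under missing at random. Neither reading stress-tests the assumption.

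**4. Time limit.** Maintenance is Days 15 to 70, or 56 days. Visit 3 is Day 43. Days 44 to 70 are 27 days, and 27/56 = 48%. Stops in that stretch are outside the list for any reason.

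**5. Is there anything to impute?** Weekly seizure frequency is the count divided by days with non-missing counts, times 7. One Maintenance entry therefore gives a value of y, and mITT requires at least one. The printed code imputes active rows only where y or y0 is missing. No visible text declares y, or its post-stop part, missing for the listed subjects.

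**6. The printed row filter, applied to every pattern.**

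| Arm | y0 and y both present | Any value missing |
|---|---|---|
| Placebo | kept | dropped |
| Either active arm | dropped | kept, whatever the reason or date of stopping |

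The visible call thus shows active subjects being imputed from complete placebo subjects. It does not show placebo imputation, selection on the MNAR list, or the return of active subjects with observed values before the ANCOVA.

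**7. Scale.** The documents do not split dropout by reason, so f, the share of an active arm with a placebo-like RRatio, is an assumption. Difference = -20 × (1 - f). SE = 34 × √(2/n): 6.80 at n = 50 and 7.60 at n = 40.

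| f | Difference | Shift | Shift/SE, n = 50 | Shift/SE, n = 40 |
|---|---|---|---|---|
| 5% | -19 | 1 | 0.15 | 0.13 |
| 10% | -18 | 2 | 0.29 | 0.26 |
| 20% | -16 | 4 | 0.59 | 0.53 |

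The last row supposes that every planned dropout is a tolerability stop with no benefit at all.

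**The case against.** **The code.** A reader might infer from step 6 that the code contradicts the text on placebo. The documents do not establish that. The sentence introducing the code breaks off in the available copy, and Section 9.5, where the MNAR cases are to be recorded, was not available. A separate placebo step, the selection of cases and a later merge may all be set out there or in the construction of the input dataset. This objection stands: it is a point to check, not a proven error.

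**The reason list.** Seizure events and lack of efficacy are tied to the outcome, whereas a tolerability stop need not depend on unobserved seizures. Some intolerability stops may also be recorded as withdrawal by subject. Both points are fair, but the second depends on how sites code the reason, and the section's title promises more than outcome-driven stops.

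**The Week 6 limit.** A subject who stops on Day 43 has Days 15 to 42 observed, 28 of 56 days, so the limit can be read as restricting imputation to those with at most about half of Maintenance. That has force against discarding data: a Day 69 stop leaves 54 of 56 days observed. It does not justify leaving later stops untested.

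**The de facto analysis may yield little.** Follow-up after stopping is only where possible (Protocol 7.3), and early terminators begin the taper at once (Protocol Table 2, note e). Post-stop days therefore mix taper and off-drug time. This limits the analysis but does not explain its silent absence. Diary recording is planned through Visit 6 (Protocol 8.1).

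**A hypothetical estimand is legitimate, and the SAP calls the trial exploratory.** Agreed. That bears on how serious the point is, not on whether a protocol commitment can lapse without a record.

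**Conclusion.** The point holds in this form. The protocol's de facto sensitivity analysis is missing from the visible SAP without explanation. The only discontinuation analysis omits stops recorded as non-seizure adverse events, ends at Week 6, and does not say what is imputed for the subjects it does list. The same gaps pass to both key secondary endpoints. For the responder endpoint, counting subjects with more than 80% missing entries as non-responders (SAP 5.10.2) gives partial cover, but it does nothing for the RRatio.

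A reader might also infer that the primary estimate is biased by 1 to 4 points. The documents do not support this. Those figures rest on assumed shares and full reversion to placebo, and they describe a different estimand from the one in 5.8.2. They show only that the untested assumption could matter by 0.13 to 0.59 standard errors.

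Confidence is moderate. The missing de facto analysis and the reason list are plain on the page; the imputation details depend partly on text that could not be seen.

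**What to change.** 1. Restore the de facto analysis of the RRatio, using eDiary data collected after discontinuation within the planned Maintenance window. State how taper days and off-drug days enter T, and report by arm how much of these data exists.
2. Add discontinuation for any adverse event to the 5.8.4.3 list. For stops after Visit 3, keep the observed on-treatment days and impute only the remaining Maintenance time from placebo. With d observed days, T = [d × observed rate + (56 - d) × imputed rate]/56. A Day 69 stop (d = 54) then gives the imputed part a weight of 2/56 = 4%, and a Day 44 stop (d = 29) a weight of 27/56 = 48%.
3. State which part of y is treated as missing for the listed subjects, separately from the 50% diary rule in 5.8.4.2.
4. Check that the full code agrees with the text: missing placebo values imputed from placebo, imputation limited to the MNAR list, and active subjects with observed values returned before the ANCOVA.
5. Carry the result into 5.9.4 and 5.10.3.

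The cost is SAP wording and some programming before database lock, with no new data collection. Post-stop data may be sparse, and the sensitivity estimate may be less favourable than the primary one.

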1.2. Sample Size Considerations

Approximately 214 subjects will be screened to achieve 150 subjects randomly assigned to treatment (50 per group) and 120 evaluable subjects for an estimated total of 40 evaluable subjects per treatment group.

A sample size of 50 subjects per group (total of 150 subjects) will provide at least 80% power to detect a difference in the means of the primary outcome measure (RRatio) of -20 (PASS 2008 Tests of Two Means, Two Sample T-Test, 2-sided alpha level = 0.1, Standard Deviation=34, and a 20% dropout rate). Approximately 214 subjects will be screened to achieve 150 subjects randomized.

In the event of higher than anticipated early terminations due to COVID-19 or other reasons, Cerevel may extend enrollment in order to maintain the planned statistical power.

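### In SAP 5.8.4.3 the jump-to-reference text and code select different subjects, and the code's filter keeps every active subject with observed data out of the data set that is analysed

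*SAP*

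**What the plan says.** SAP 5.8.4.3 treats certain discontinuations up to Visit 3 (seizure AE, subject withdrawal, lack of efficacy, loss to follow-up) as potentially missing not at random. These subjects are to be listed in Section 9.5 before database lock and imputed by jump to reference. The method is given as "the missing values in each of the active group will be imputed using the multiple imputation procedure described above", except that active-arm values are drawn from observed placebo data. Missing placebo values are also to be imputed from placebo.

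The PROC MI step reads the data set mcmc1 through a filter. An active subject is kept if "y = . or y0=.) and trt ne 'Placebo" is met, that is, if the log Maintenance rate (y) or the log baseline rate (y0) is missing. A placebo subject is kept only if both are present. The output is Out1X. The next instruction sends each imputed data set to the ANCOVA of 5.8.3 and then to PROC MIANALYZE.

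Three other provisions decide who can have a missing rate:

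- SAP 5.2, Table 10: the mITT requires a recorded baseline frequency with at least 20% diary compliance, and "at least 1 post baseline entry in the seizure diary during maintenance phase".
- SAP 3.1.1 and 5.8.2: the rate is seizures divided by days with non-missing counts, times 7, using only data from before treatment discontinuation.
- SAP 5.8.4.2, the procedure referred to: it "will be utilized based on the mITT population", and a period's rate becomes missing when more than half of its diary entries are missing.

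**The concern.** There are two separate faults.

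The first is the trigger. The text selects by reason and timing of stopping, and the code selects by a missing rate. These are different sets of subjects, and no sentence visible in 5.8.4.3 turns a listed subject's rate into a missing one.

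The second is the filter. Restricting the PROC MI input to donors and recipients is a reasonable way to impute. But the restricted output is then analysed as if it were the trial data. Active subjects with observed rates never enter it. Neither do placebo subjects with a missing value, although the text says these are imputed. The code in 5.8.4.2 has no filter, so there the same instruction to analyse each data set works.

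At stake is the only analysis that asks whether informative early stopping could explain a result on the primary endpoint. SAP 5.9.4 and 5.10.3 reuse it for both key secondary endpoints, so one coding fault affects three robustness checks.

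**Working it through.** **The plan's own figure.** SAP 1.2 claims 80% power or more for an RRatio difference of −20 with 50 randomised per arm. Its assumptions are "2-sided alpha level = 0.1, Standard Deviation=34, and a 20% dropout rate". 50 × (1 − 0.20) = 40 evaluable per group. The standardised difference is 20 / (34 × √(2/40)) = 2.63, which gives 83.8% power by the normal approximation and 83.2% by the noncentral t with 78 df. The claim reproduces. Nothing below changes it; it only supplies 40 per arm as a convenient size for an illustration.

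**Step 1: can a listed early stopper in the mITT have a missing rate under the primary derivation?** Membership needs at least one Maintenance entry. One usable day makes the denominator of the Maintenance rate at least 1, so y exists. The baseline condition ensures that y0 exists. The code's condition is then false, and the subject is not selected.

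**Step 2: does the 50% rule of 5.8.4.2 change that?** By SAP Table 3, Maintenance runs from Day 15 to the day before Day 71, so planned days = 71 − 15 = 56. Early termination on Day d ends the period the day before, leaving d − 15 days. Assume a complete diary up to that point.

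| Early termination | Days observed | Missing, planned-day denominator | Missing, participation-time denominator |
|---|---|---|---|
| Day 42 | 27 of 56 | 29/56 = 51.8% | about 0% |
| Day 43 (Visit 3) | 28 of 56 | 28/56 = 50.0% | about 0% |

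With planned days as the denominator, stopping by Day 42 meets the rule. Stopping on Day 43 does not, although the text includes Visit 3. With actual participation time, the basis that SAP 5.7.1 uses for diary compliance, a compliant early stopper never meets it. The SAP does not say which denominator applies, or that the rule carries over to 5.8.4.3.

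**Step 3: what does the filter pass on?** Illustration with assumed numbers: 40 mITT subjects per arm, of whom 4 per arm stop between Days 22 and 31.

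| How y is set | Missing y | Placebo in Out1X | Active in Out1X | Observed active left out | Placebo with missing y left out |
|---|---|---|---|---|---|
| Primary derivation | 0 | 40 | 0 | 80 | 0 |
| Early stoppers' rates set to missing (planned-day rule or Section 9.5 list) | 12 | 36 | 4 + 4 = 8 | 2 × 36 = 72 | 4 |

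In the first case the ANCOVA has no active arm. In the second, the active subjects are only those whose values were drawn from the placebo model, so the expected difference is close to zero by construction, whatever the drug does. The planned effect is −20.

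**The case against.** The strongest reply is that 5.8.4.3 should be read as a whole. It adopts the procedure described above it, which includes the 50% rule, and both code blocks read mcmc1. Visit 3 falls at the midpoint of Maintenance, so a planned-day rule would catch almost all subjects who stop before it. The text also says that the subjects listed in Section 9.5 are imputed, which implies that their rates are set to missing. Further, the sentence just before the code breaks off in the available text, and the content of Section 9.5 is not available, so a rule that cannot be seen may still exist.

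Much of this stands. A reader might infer that no mITT subject can have a missing rate, and therefore that nobody is imputed. The documents do not support that: it follows under the primary derivation, but not if the 50% rule carries over on planned days or if the listed subjects' rates are set to missing. A reader might also infer that the check simply repeats the main result, but an output holding only placebo subjects cannot reproduce a three-arm ANCOVA.

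The reply does not reach the filter. It is also fair to say that an ANCOVA with a missing or tiny active arm would be noticed, that SAP 9.7 requires independent programming, and that 5.8.3 calls for dose-versus-placebo contrasts. These make it likely that the fault would be found. But the repair would then be chosen after the SAP is final, and programmers could choose differently.

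**Conclusion.** The point holds in two parts of different strength.

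- **Filter: holds on every reading considered.** As printed, all active subjects with observed y and y0, and all placebo subjects with a missing value, are outside Out1X, and no visible step adds them back. The check either has no active arm or compares observed placebo with placebo-imputed values. Neither says anything about informative stopping.
- **Trigger: holds as a mismatch between text and code.** Under the primary derivation, a listed early stopper with one usable Maintenance day is not selected. Whether the 50% rule would select that subject depends on a carry-over and a denominator that the SAP leaves open.

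This rests on the SAP's mITT. The mITT in Protocol 9.3 is wider and could include subjects with no Maintenance rate, but SAP Table 10 governs this analysis. The counts of 0, 8 and 72 depend on the assumed 40 and 4 per arm. The exclusion itself does not. The number of subjects actually listed in Section 9.5 cannot be checked.

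The correction should be made before database lock. The primary analysis, sample size and power are not affected.

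**What to change.** Amend SAP 5.8.4.3, and through it the analyses in 5.9.4 and 5.10.3, as follows:

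1. State that the Maintenance rate of each subject listed in Section 9.5 is set to missing for this analysis, and that the list, not diary compliance, decides who is imputed from placebo. If the 50% rule is also meant to apply here, say so and give its denominator.
2. Let placebo subjects with a missing value into the PROC MI step, so that they are imputed from observed placebo data as the text says.
3. Append all other active and placebo subjects with observed data to each imputed data set before the ANCOVA and PROC MIANALYZE.

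The cost is a few sentences and a short data step, with no new data. The sensitivity estimate may be less favourable to the drug than the main one. Moving the analysis to all treated subjects, or building a day-weighted mix of observed and imputed Maintenance time, would be a design choice beyond what this correction needs.
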